Subjects with prolactinomas who are resistant to dopamine agonist therapy who manifest continued tumor size growth while on a dopamine agonist, unless intolerant of adequate doses of a dopamine agonist.

Subjects with malignant pituitary tumors will be eligible for the malignant pituitary tumor arm of the study regardless of existing visual deficits.

Exclusion criteria: Children will be excluded. If subjects have preexisting visual field deficits, they will be monitored on more frequent basis. Patients will also be excluded if they have left ventricular ejection fraction less than 50 %, moderate to severe hepatic impairment (see below for specifics), active hepatitis, HIV positivity, concurrent cancers, life expectancy less than one year, and pregnancy. Pregnant patients will be excluded. Childbearing age women will be required to use

contraception. Patients who become pregnant during the study should discontinue the study immediately.

Withdrawal of Subjects:

Monitoring for adverse effects: Prior to initiating therapy, patients will undergo an echocardiogram and ECG to evaluate the ejection fraction, and the echocardiogram will be repeated every 8 weeks (Visit 3, 5, and 7) and on visit 8. Patients will also undergo ophthalmic testing at visits 1, 4, and 7. Patients with pre-existing stable visual field compromise prior to enrollment will undergo visual field testing at visits 1, 2, and 3, and if stable, then they will proceed with visual field testing every three months for the duration of the study. Patients will be evaluated for adverse effects monthly with physical examinations, chemistry and hematology panels, and ECGs. Adverse events will be graded by the NCI-CTC and include: anorexia, decreased ejection fraction, interstitial lung disease/pneumonitis, diarrhea, nausea, vomiting, hepatotoxicity, rash, and fatigue. Lapatinib will be discontinued in those who developed decreased ejection fraction, who develop pulmonary symptoms, retinal toxicity, worsening of visual fields, and those with toxicity greater than or equal to Grade 2 on the NCI-CTC. [name], from Oncology department at Cedars-Sinai Medical Center, will assist us in monitoring patients for adverse events.

If at any time a patient demonstrates compromise of his visual fields, dilated retinal exam or tumor growth on MRI, he will be withdrawn from the study and referred for surgery.

Section 6.0 Treatment of Subjects

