who received lapatinib and 7% in those on placebo. Risks of adverse events are not additive or cumulative. SAEs were reported in 6% of those on lapatinib compared to 5% on placebo. Cardiac events including left ventricular ejection fraction decreases were reported in approximately 1% of patients and most have partial or full recovery. Symptomatic decreases in ejection fraction were observed in approximately 0.3% of patients on lapatinib. Interstitial lung disease is observed in 0.2% of patients. Hepatotoxicity has been observed in <1% of patients. Grade 3 and 4 diarrhea occurs in <10% of patients. Nausea may be seen in 18% of patients and rash in 29% (Investigators' Brochure).

2. Prior to initiating therapy, patients will undergo an echocardiogram and ECG to evaluate the ejection fraction, and the echocardiogram will be repeated every 8 weeks and on visit. Patients will be evaluated for adverse effects monthly with physical examinations, chemistry and hematology panels, and ECGs. Adverse events will be graded by the NCI-CTC. Common adverse events include: hand-foot syndrome, rash, diarrhea, indigestion, nausea, vomiting, anorexia, anemia, low platelets, abnormal liver tests (ALT (SGPT) level raised, AST/SGOT level raised, hyperbilirubinemia, backache, pain in limb, insomnia, fatigue, and shortness of breath. Rare but serious events include: heart failure (depression of left ventricular systolic function), abnormal heart beat (prolonged QT interval), liver damage (hepatotoxicity), and lung problems (interstitial lung disease/pneumonitis). Lapatinib will be discontinued in those who developed decreased ejection fraction, who develop pulmonary symptoms. Those subjects with toxicity less than or equal to Grade 2 on the NCI-CTC will have their dose held and resumed when the toxicity has resolved. Those subjects with toxicity equal to Grade 3 on the NCI-CTC will have their dose held and resumed at a fifty percent dose reduction when the toxicity has resolved. Those subjects with toxicity equal to Grade 4 on the NCI-CTC will be discontinued on the study drug. [name], from Oncology department at Cedars-Sinai Medical Center, will assist us in monitoring patients for adverse events.
3. If at any time a patient demonstrates a worsening of their visual fields or tumor growth on MRI, they will be withdrawn from the study and referred for surgery.

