then hold investigational product for 2 weeks, repeat liver chemistry testing in 2 weeks, and then call the Novartis Medical Monitor to discuss the possibility of re-challenging with investigational product.

If the treatment is exhibiting efficacy **and** the subject wants to continue for potential benefit of lapatinib therapy after being informed of the results of liver chemistry testing,

then the investigational product may be re-started at the reduced dose agreed upon by the investigator and the Novartis Medical Monitor. In such cases, Study Visit #8 will not take place if the decision to continue on lapatinib takes place prior to discontinuation of study drug on study. Liver chemistries and aforementioned signs and symptoms should be monitored at a minimum of every 2 weeks until resolution, stabilization, or a return to baseline values, at which point monitoring should be continued per protocol.

If a subject experiences ALT $>3 \times$ ULN **but** $<5 \times$ ULN **and** total bilirubin $\leq 2 \times$ ULN, without signs or symptoms of hepatitis or hypersensitivity, **and** who can be monitored weekly, then the following actions should be taken:

continue investigational product;
monitor weekly until liver chemistries resolve, stabilize, or return to within baseline, then monitor liver chemistries as per protocol assessment schedule;
if ALT >3 and $< 5 \times$ ULN for > 4 weeks, discontinue the treatment;
if at any time this subject meets any of the aforementioned liver chemistry stopping criteria, then proceed as described above.

Liver Chemistry Follow up Criteria

For all subjects who meet any of the liver chemistry criteria described above, make every attempt to carry out the liver event follow up assessments described below:

Viral hepatitis serology including:

- Hepatitis A IgM antibody;
- Hepatitis B surface antigen and Hepatitis B Core Antibody (IgM);
- Hepatitis C RNA;
- Cytomegalovirus IgM antibody;
- Epstein-Barr viral capsid antigen IgM antibody (or if unavailable, obtain heterophile antibody or monospot testing);
- Hepatitis E IgM antibody (if subject resides or has traveled outside USA or Canada in past 3 months);

Serum creatine phosphokinase (CPK) and lactate dehydrogenase (LDH);

Complete blood count with differential to assess eosinophilia;

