Non-hematological, Grade 3 or 4	Apply maximum supportive care recommendations (see section Error! Reference source not found.) Hold lapatinib therapy until recovery to Grade \leq 1 (up to 14 days). Refer to events management instructions Section Error! Reference source not found. Grade 3 or 4 left ventricular cardiac dysfunction - please refer to specific section Error! Reference source not found. For NCI-CTCAE v3.0 Grade 3 or 4 interstitial pneumonitis or Grade 4 rash manifested as toxic epidermal necrolysis (e.g. Stevens-Johnson Syndrome etc) lapatinib must be permanently discontinued If recurrence of adverse event after drug hold / interruptions is observed, and maximum supportive care measures applied, a dose reduction by 250mg is recommended. Lapatinib should not be used at doses below 1000mg if given as monotherapy or 750mg in combination with trastuzumab. NOTE: The 750 mg dose should only be used after all supportive measures have been exhausted. (If administered in combination with paclitaxel refer to table 13)
Non-hematological, Grade 3 or 4 and adverse events NOT resolved to Grade \leq 2 within a maximum of 2 weeks from last planned administration	Action (discontinue or resume lapatinib therapy) in individual cases to be decided by the Executive Committee. Dose reductions by 250mg (up to 2 reductions) will be considered after maximum supportive care recommendations (see Error! Reference source not found.) are introduced.

Cardiac* (asymptomatic drop in LVEF or symptomatic congestive heart failure)
	
Lapatinib therapy to be discontinued permanently in case of symptomatic NYHA class III and IV CHF. Lapatinib therapy to be hold continued or resumed according to Figure 1 for patients with NYHA class I or II CHF.

Hematological adverse events: Absolute neutrophil count (ANC) <1.0 x 10⁹/L Platelets <75 x 10⁹/L Hemoglobin <9.0 g/dL (after transfusion if needed)
	
Hold chemotherapy if lapatinib given simultaneously; if the adverse event is related to chemotherapy please refer to appropriate label (until recovery to Grade ≤1). If ANC recovers to 1.5 x 10⁹/L within 7days, then merely delaying dose is acceptable. If no recovery to ANC of 1.5 x 10⁹/L within 7 days then decrease chemotherapy dose by 20%. Dose modifications for thrombocytopenia, at the start of subsequent courses of therapy are the same as recommended for neutropenia above. Next cycle should not begin until the platelet count has recovered to 100 x 10⁹/L or more.

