	
In case of multiple short interruptions of dose due to either adverse events or drug supply or other reasons the sum of days without lapatinib treatment should not exceed 21 days in any 90 day treatment period.

*Severity corresponding to NYHA criteria

RECOMMENDED ELEMENTS OF A SCIENTIFIC PROTOCOL
(Noted sections should only be included as applicable to your research)

29

Dose Delays and Dose Reductions

Treatment may be delayed, up to 2 weeks, to allow for resolution of toxicity except in the event of NCI CTCAE Grade 3 or 4 left ventricular cardiac dysfunction or NCI CTCAE Grade 3 or 4 interstitial pneumonitis (See Criteria for Evaluating Cardiac and Respiratory Events). The Investigator must consult the Novartis Medical Monitor prior to continuing therapy for any subject requiring a delay of more than 2 weeks for unresolved toxicity, but in general, such subjects should be withdrawn from the study. If treatment is delayed for reasons other than toxicity (i.e., unplanned travel or vacation, or lack of transportation to the site) and the subject has insufficient investigational product available, the subject should resume the usual dosing schedule once drug supply has been made available. However, if the subject has been off therapy for more than 2 weeks, the Investigator must consult the Novartis Medical Monitor prior to continuing therapy.

Dose reduction for drug-related toxicity is permitted; however the Novartis Medical Monitor must be consulted prior to implementing any change in dosing. Only one dose reduction is permitted per subject and subjects should not be rechallenged to a higher dose level. If a NCI CTCAE Grade 3 or 4 drug-related event (other than left ventricular cardiac dysfunction or interstitial pneumonitis) has occurred, the investigator may discuss with the Novartis Medical Monitor whether a reduction of dose is appropriate.

PHARMACEUTICAL INFORMATION

Lapatinib (NSC #727989)

Chemical Name: N-{3-Chloro-4-[(3-fluorobenzyl)oxy]phenyl}-6-[5-{{[2-(methylsulfonyl)ethyl]amino}methyl)-2 furyl]-4-quinazolinamine,

Other Names: None

Mode of Action: Dual inhibitor of epidermal growth factor receptor (EGFR or ErbB1) and ErbB2 tyrosine kinases.

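### For a Grade 4 ALT rise above 8 × ULN with bilirubin at or below 2 × ULN, the general rules discontinue lapatinib but the liver section allows a restart, with no precedence stated

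*Combined protocol and SAP*

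**What the plan says.** Several parts of the protocol speak to the same event.

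- **Section 5.0, Withdrawal of Subjects.** Lapatinib is stopped in, among others, "those with toxicity greater than or equal to Grade 2 on the NCI-CTC".
- **Section 8.0, item 2.** "Those subjects with toxicity equal to Grade 4 on the NCI-CTC will be discontinued on the study drug". Grade 3 subjects "will have their dose held and resumed at a fifty percent dose reduction when the toxicity has resolved".
- **Section 8.0, Liver Chemistry Stopping Criteria.** The drug is stopped at once and for good only when ALT above 3 × ULN comes with bilirubin above 2 × ULN. Three other triggers lead to a hold: ALT above 8 × ULN, ALT above 5 × ULN for at least 2 weeks, or ALT above 3 × ULN with symptoms. For these the instruction is "then hold investigational product for 2 weeks, repeat liver chemistry testing in 2 weeks, and then call the Novartis Medical Monitor". If the drug is working and the informed subject wants to go on, "then the investigational product may be re-started at the reduced dose agreed upon by the investigator and the Novartis Medical Monitor".
- **Table 1, non-hematological Grade 3 or 4.** "Hold lapatinib therapy until recovery to Grade" 1 or lower, for up to 14 days. If the event has not come down to Grade 2 or lower within 2 weeks, stopping or resuming is "in individual cases to be decided by the Executive Committee".
- **Dose Delays and Dose Reductions.** "If a NCI CTCAE Grade 3 or 4 drug-related event (other than left ventricular cardiac dysfunction or interstitial pneumonitis) has occurred", the investigator may discuss a dose reduction with the Medical Monitor. Toxicity unresolved after 2 weeks generally means withdrawal.

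**The concern.** A site facing a Grade 4 ALT rise finds one rule that ends treatment and another that opens a path back to it. The general rules turn on toxicity grade. The liver rules turn on multiples of ULN and do not mention grade. The two systems overlap, and no sentence ranks them.

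The protocol counts every Grade 4 laboratory abnormality as a serious adverse event (Additional SAE definitions), so the conflict concerns an event of recognised severity. There are three sites, and the decision is whether to give a hepatotoxic drug again. The Medical Monitor's agreement is a real safeguard, but the liver section gives the monitor no criterion to apply. The DSMB oversees safety in general and has no stated part in individual restarts.

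**Working it through.** No published figure needs reproducing; the main check is a comparison of texts.

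**1. Test case.** Grade 4 ALT above 8 × ULN, bilirubin at or below 2 × ULN, efficacy shown, subject willing, current dose 1250 mg.

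| Source | Outcome |
|---|---|
| Section 5.0 | Discontinue |
| Section 8.0 item 2 | Discontinue |
| Liver Chemistry Stopping Criteria | Hold 2 weeks, retest, may restart at a reduced dose |
| Dose Delays and Dose Reductions | Medical Monitor; in general withdraw if unresolved after 2 weeks |
| Table 1 | Hold to Grade 1 or lower for up to 14 days; Executive Committee if not Grade 2 or lower |

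The direct contradiction is between the first two rows and the third. Table 1 differs only in part, and the Dose Delays text is compatible with the liver section.

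**2. Does this depend on the Grade 4 cut-off?** The documents give none. The ALT trigger is unbounded above, so it overlaps Grade 4 wherever the cut-off lies. Assumed cut-offs of 5, 8, 10, 15, 20 and 30 × ULN all overlap; at 8 × ULN or more, every Grade 4 value falls inside the trigger.

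**3. Is precedence stated?** Section 8.0 item 1 says only that more detail follows. The Other adverse events paragraph begins by referring to any other Grade 3 or 4 event, which separates it from the event-specific sections. Neither names Section 5.0 or item 2. The Safety text after the liver follow-up criteria still carries a drafting instruction to insert a cross-reference to those criteria.

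**4. Recovery before restart.** Item 2 (Grade 3) and Table 1 require it. The liver restart paragraph names efficacy, the subject's wish and an agreed dose, but no ALT or bilirubin value. If the hold triggers are reapplied at the retest, ALT still above 5 × ULN or symptoms would mean a further hold. The missing value then matters mainly for asymptomatic ALT up to 5 × ULN.

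**5. How often.** Inputs: 2% Grade 4 ALT/AST on monotherapy (Liver Chemistry Stopping Criteria) and 30 non-malignant subjects (Section 9.0).

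- Expected events: 30 × 0.02 = 0.6.
- Chance of at least one: 1 − 0.98^30 = 0.4545, or 45%.
- Assumed range of rates: 1 − 0.99^30 = 0.260 at 1%; 1 − 0.97^30 = 0.599 at 3%.

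Restart also needs efficacy. As an illustration, take efficacy to mean response at the 20% to 40% used in Section 9.0, independent of the ALT rise:

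- Expected cases: 0.6 × 0.20 = 0.12 to 0.6 × 0.40 = 0.24.
- Chance of at least one: 1 − (1 − 0.02 × 0.20)^30 = 0.113 to 1 − (1 − 0.02 × 0.40)^30 = 0.214.

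AST-only rises, subjects with bilirubin above 2 × ULN and unwilling subjects would lower this. A broader meaning of efficacy would raise it.

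**6. Restart dose.** 1250 − 250 = 1000 mg, which meets the 1000 mg monotherapy floor (Other adverse events, Table 1). The next 250 mg tablet step, 750 mg, does not. Item 2's half dose is 1250 × 0.5 = 625 mg, which is 2.5 tablets and below the floor.

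**The case against.** The best reply is that a specific section governs a general one. The liver section, Table 1, the Other adverse events text and the Dose Delays text all allow hold-and-resume at Grade 4, so the general lines in Section 5.0 and item 2 are the outliers. The omission of liver from the exceptions in Dose Delays supports this: those exceptions withdraw permission to delay or reduce, so leaving liver out fits the liver section. This is a reasonable guess at intent. It remains a drafting convention that the protocol does not state, and it does not reconcile a mandatory stop with a permitted restart.

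Other parts of the reply stand and limit the point.

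- A reader might infer that one site could stop and another restart with both in compliance. The text does not support that. Stopping satisfies both rules, because restart is only permitted; restarting breaches item 2.
- A reader might infer that the liver section authorises restart before recovery. It requires a hold, a retest and Medical Monitor agreement, and is silent on a recovery value. Item 2 and Dose Delays can be read alongside it, and the Appendix 3 algorithm may give a value. This is a gap, not a contradiction. Appendix 3 would settle the Grade 4 conflict only if it also stated precedence.
- Letting the liver section govern every liver event would do harm. All its triggers need an ALT rise, so isolated Grade 3 or 4 AST or bilirubin rises would lose the rules that now cover them. Asymptomatic ALT of 5 to 8 × ULN for under 2 weeks would have only a retest.

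**Conclusion.** The contradiction is real and narrow: Grade 4 ALT above 8 × ULN with bilirubin at or below 2 × ULN. It should be corrected because it concerns an SAE-level toxicity and the correction is small. The absent recovery value is secondary and provisional, since the Appendix 3 figure is not available.

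The 45% should not be read as the probability of a restart conflict. It is an upper bound for the 30 planned subjects at the cited 2% rate, since it counts every Grade 4 ALT or AST rise. It assumes that the monotherapy rate carries over to 6 months of treatment in this population and that subjects are independent. The documents give no size for the malignant arm, whose subjects would add to the count, and no rate of actual restarts.

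**What to change.** 1. Add to the restart paragraph of the liver section: Grade 4 ALT is not re-challenged; other subjects may restart only when ALT and bilirubin have recovered to Grade 1 or lower or to baseline, at 1000 mg. The Grade 4 bar comes from Section 8.0 item 2, and the recovery standard from Table 1 and the Other adverse events text. A subject already at 1000 mg has no lower permitted dose and would not restart.
2. State that the liver section, so amended, takes precedence over Section 5.0, Section 8.0 item 2 and Table 1 only for ALT rises that meet one of its hold or stop triggers: ALT above 3 × ULN with bilirubin above 2 × ULN, ALT above 8 × ULN, ALT above 5 × ULN for at least 2 weeks, or ALT above 3 × ULN with symptoms. Item 2 and Table 1 continue to apply to all other liver abnormalities, including isolated AST or bilirubin rises and ALT rises below those triggers.

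The cost is two sentences in an amendment, with no new subjects, tests or visits. A few discretionary restarts are lost, including for a responding patient with Grade 4 ALT. If the sponsor prefers to keep that option, Section 5.0 and item 2 must be amended to allow it, so an edit is needed either way. The wider disagreement among Section 5.0, item 2 and Table 1 for other toxicities is not settled by these edits.

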Appendix: Liver Chemistry Stopping and Follow up Criteria

- bilirubin fractionation should be performed if testing is available. If testing is unavailable and a subject meets the criterion of total bilirubin $>2.0 \times \text{ULN}$, then the event should still be reported as an SAE and actions taken as described
- the appearance or worsening of fatigue, nausea, vomiting, right upper quadrant pain or tenderness, fever, rash, or eosinophilia
- once liver chemistries resolve, stabilize, or return to baseline, then continue monitoring per the protocol assessment schedule
- retest within 3 days from the first occurrence and then weekly to determine if ALT elevation persists

Dermatologic (skin) adverse events

Rash has been reported in 29% of patients on lapatinib monotherapy with significant skin adverse events (Grade 3 or more) resulting in 1-3%. For NCI-CTCAE v3.0 Grade 4 rash manifested as toxic epidermal necrolysis (i.e. Stevens-Johnson's Syndrome etc) lapatinib must be permanently discontinued. Subjects with poorly tolerated skin adverse events may be successfully managed by providing a brief (up to 14 days) therapy interruption; the daily dose of lapatinib

should then be reinstated. However, the rash may improve without the need for interrupting therapy with lapatinib. Of note in current studies, many subjects were able to resume lapatinib therapy at the same dose after resolution of rash, and they then had less extensive and/or severe rashes. A variety of agents can be used to manage skin rashes. These include mild-to-moderate strength steroid creams, topical or systemic antibiotics, topical or systemic antihistamines, and occasionally, retinoid creams.

There is no standard, known, or established treatment proven effective for drug-related skin rashes or changes due to lapatinib. If the rash is severe (1-3%) then most commonly, a papular/pustular rash has been observed, which frequently improves even though the same dose of lapatinib therapy is continued uninterrupted. The need for oral or topical antibiotics is a clinical decision of the investigator and should be preceded by a culture of affected areas and, if indicated, a dermatology consultation. Oral retinoids should not be given because of theoretical concerns about negatively affecting the lapatinib mechanism of action. Oral steroids are also strongly discouraged. Other options for treatment of significant rashes may be determined upon consultation with dermatologist.

Gastrointestinal adverse events

Overall 48% of patients on lapatinib monotherapy (n= 1573) experienced diarrhea, with grade 3 diarrhea reported in 21% of subjects and grade 4 diarrhea in 7%. If GI adverse events are not appropriately managed, they may be associated with the development of dehydration. Management of gastrointestinal adverse events is discussed in detail in below.

Nausea, vomiting, or both

Nausea was reported in 18% of patients on lapatinib monotherapy (n=1573). In subjects who have emesis and are unable to retain lapatinib, every attempt should be made to obtain control of nausea and vomiting. A dose may be repeated if tablets can be visually found after the vomiting episode.

Diarrhea

These broad general management principles are recommended to proactively try and avoid more serious complications by active management of diarrhea syndrome. Guidelines such as these should never replace sound clinical judgment. Experience thus far suggests that when lapatinib is used as monotherapy, uncomplicated Grade 1 or 2 diarrhea is most prevalent. These general management principles do not address comprehensive management of more serious or protracted diarrhea syndromes.

Common clinical sense with the onset of uncomplicated Grade 1-2 diarrhea: stop all lactose containing products: drink 8-10 large glasses of clear liquids a day; eat frequent small meals; for Grade 2 diarrhea hold cytotoxic chemotherapy, and consider a dose reduction of lapatinib (discuss with medical monitor); administer standard doses of loperamide: initial dose 4 mg followed by 2 mg every 4 hours or after every unformed stool. It is suggested to continue loperamide until the subject is free from diarrhea for 12 hours.

For Grade 3 or 4 diarrhea or Grade 1 or 2 with complicating features (severe cramping, severe nausea/vomiting, decreased performance status, fever, sepsis, Grade 3 or 4 neutropenia, frank bleeding, dehydration) use intravenous fluids as

appropriate, consider hospital administration. Use prophylactic antibiotics as needed (example fluoroquinolones) especially if diarrhea is persistent beyond 24 hours or there is a fever or Grade 3-4 neutropenia, hold both cytotoxic chemotherapy and lapatinib and discuss with medical monitor.

Treatment of gastrointestinal adverse events

Diarrhea can be debilitating, and on rare occasions, it is potentially life-threatening. Based on experience with lapatinib alone or in combination with taxanes and/or trastuzumab, diarrhea should be managed proactively to avoid complications or worsening of the patient's condition. Guidelines developed by an American Society of Clinical Oncology (ASCO) panel for treating chemotherapy-induced diarrhea are abstracted below.

Pharmacological approaches include the following:

Loperamide, administered as an initial 4-mg dose, followed by 2-mg doses every 4 hours. This dose and regimen are moderately effective.

Clonidine, non-steroidal anti-inflammatory drugs, and the serotonin antagonist cyproheptadine have been shown to be effective in controlling diarrhea associated with inflammation of the bowel.

The synthetic octapeptide, octreotide, has been shown to be effective in the control of diarrhea induced by fluoropyrimidine-based chemotherapy regimens when administered as an escalating dose by continuous infusion or subcutaneous injection. Octreotide can be administered at doses ranging from 100 µg twice daily to 500 µg 3 times daily, with a maximum-tolerated dose of 2000 µg 3 times daily in a 5-day regimen.

Management of interstitial lung disease

Pulmonary events occur in approximately 0.2% of patients. If a patient develops symptoms suggestive of interstitial pneumonitis, adult respiratory distress syndrome (ARDS), or non-cardiogenic pulmonary edema, lapatinib or trastuzumab therapy should be interrupted and a thorough evaluation performed. If NCI-CTCAE v3.0 Grade 3 or 4 pneumonitis/fibrosis or pulmonary infiltrate is confirmed (and the relationship to lapatinib and/or trastuzumab cannot be excluded), lapatinib and/or trastuzumab must be permanently discontinued. All incidences of interstitial lung disease/ interstitial pneumonitis regardless of grade must be reported as serious adverse events (SAEs).

Other adverse events

For any other NCI-CTCAE v3.0 Grade 3 or 4 adverse events or any clinically significant, lower-grade adverse event, treatment with lapatinib should be interrupted for a maximum of 14 days until the patient recovers completely or the adverse event reverts to NCI-CTCAE v3.0 Grade 1 or to baseline grade. If recurrence of adverse event after drug holiday / interruptions is observed a dose reduction by 250mg is recommended. Dose reduction should only be implemented when all supportive care measures have been exhausted without an improvement of patient status. Lapatinib should not be used at doses below 1000mg if given as monotherapy or 750mg in combination with trastuzumab. In all cases where the subject is withdrawn due to unusual or unusually severe adverse event considered related to lapatinib, the investigator must report the withdrawal as an SAE and on the CRFs.

Table 1 Summary of dose holding/interruptions and dose de-escalation recommendations for GW572016 (lapatinib) in case of lapatinib related adverse events (graded according to NCI-CTCAE v3.0)

Adverse events	Action
Non-hematological, Grade 1 or 2	Continue lapatinib therapy at full dose prescribed (see adverse events management instructions section Error! Reference source not found. Apply maximum supportive care recommendations (see Error! Reference source not found.) If prolonged duration of Grade 2 adverse event is affecting quality of life a one-time decrease of dose by 250 mg is allowed.
Non-hematological, Grade 3 or 4	Apply maximum supportive care recommendations (see section Error! Reference source not found.) Hold lapatinib therapy until recovery to Grade \leq 1 (up to 14 days). Refer to events management instructions Section Error! Reference source not found. Grade 3 or 4 left ventricular cardiac dysfunction - please refer to specific section Error! Reference source not found. For NCI-CTCAE v3.0 Grade 3 or 4 interstitial pneumonitis or Grade 4 rash manifested as toxic epidermal necrolysis (e.g. Stevens-Johnson Syndrome etc) lapatinib must be permanently discontinued If recurrence of adverse event after drug hold / interruptions is observed, and maximum supportive care measures applied, a dose reduction by 250mg is recommended. Lapatinib should not be used at doses below 1000mg if given as monotherapy or 750mg in combination with trastuzumab. NOTE: The 750 mg dose should only be used after all supportive measures have been exhausted. (If administered in combination with paclitaxel refer to table 13)
Non-hematological, Grade 3 or 4 and adverse events NOT resolved to Grade \leq 2 within a maximum of 2 weeks from last planned administration	Action (discontinue or resume lapatinib therapy) in individual cases to be decided by the Executive Committee. Dose reductions by 250mg (up to 2 reductions) will be considered after maximum supportive care recommendations (see Error! Reference source not found.) are introduced.

Cardiac* (asymptomatic drop in LVEF or symptomatic congestive heart failure)
	
Lapatinib therapy to be discontinued permanently in case of symptomatic NYHA class III and IV CHF. Lapatinib therapy to be hold continued or resumed according to Figure 1 for patients with NYHA class I or II CHF.

Hematological adverse events: Absolute neutrophil count (ANC) <1.0 x 10⁹/L Platelets <75 x 10⁹/L Hemoglobin <9.0 g/dL (after transfusion if needed)
	
Hold chemotherapy if lapatinib given simultaneously; if the adverse event is related to chemotherapy please refer to appropriate label (until recovery to Grade ≤1). If ANC recovers to 1.5 x 10⁹/L within 7days, then merely delaying dose is acceptable. If no recovery to ANC of 1.5 x 10⁹/L within 7 days then decrease chemotherapy dose by 20%. Dose modifications for thrombocytopenia, at the start of subsequent courses of therapy are the same as recommended for neutropenia above. Next cycle should not begin until the platelet count has recovered to 100 x 10⁹/L or more.

	
In case of multiple short interruptions of dose due to either adverse events or drug supply or other reasons the sum of days without lapatinib treatment should not exceed 21 days in any 90 day treatment period.

*Severity corresponding to NYHA criteria

RECOMMENDED ELEMENTS OF A SCIENTIFIC PROTOCOL
(Noted sections should only be included as applicable to your research)

29

Dose Delays and Dose Reductions

Treatment may be delayed, up to 2 weeks, to allow for resolution of toxicity except in the event of NCI CTCAE Grade 3 or 4 left ventricular cardiac dysfunction or NCI CTCAE Grade 3 or 4 interstitial pneumonitis (See Criteria for Evaluating Cardiac and Respiratory Events). The Investigator must consult the Novartis Medical Monitor prior to continuing therapy for any subject requiring a delay of more than 2 weeks for unresolved toxicity, but in general, such subjects should be withdrawn from the study. If treatment is delayed for reasons other than toxicity (i.e., unplanned travel or vacation, or lack of transportation to the site) and the subject has insufficient investigational product available, the subject should resume the usual dosing schedule once drug supply has been made available. However, if the subject has been off therapy for more than 2 weeks, the Investigator must consult the Novartis Medical Monitor prior to continuing therapy.

Dose reduction for drug-related toxicity is permitted; however the Novartis Medical Monitor must be consulted prior to implementing any change in dosing. Only one dose reduction is permitted per subject and subjects should not be rechallenged to a higher dose level. If a NCI CTCAE Grade 3 or 4 drug-related event (other than left ventricular cardiac dysfunction or interstitial pneumonitis) has occurred, the investigator may discuss with the Novartis Medical Monitor whether a reduction of dose is appropriate.

PHARMACEUTICAL INFORMATION

Lapatinib (NSC #727989)

Chemical Name: N-{3-Chloro-4-[(3-fluorobenzyl)oxy]phenyl}-6-[5-{{[2-(methylsulfonyl)ethyl]amino}methyl)-2 furyl]-4-quinazolinamine,

Other Names: None

Mode of Action: Dual inhibitor of epidermal growth factor receptor (EGFR or ErbB1) and ErbB2 tyrosine kinases.

How Supplied: lapatinib is supplied as 250 mg oval, biconvex, orange film-coated tablets with one side plain and the opposite side debossed with FG HLS. The tablets contain 410 mg of lapatinib Ditosylate Monohydrate, equivalent to 250 mg lapatinib free base per tablet. The tablets are packaged into HDPE bottles with child-resistant closures.

Excipients present in the tablet include: Microcrystalline cellulose, povidone, sodium starch glycolate, and magnesium stearate.

The film-coat contains: Hydroxypropyl methylcellulose, titanium dioxide, triacetin/glycerol triacetate, and yellow iron oxide.

Storage: The intact bottles should be stored at controlled room temperature (15°C-30°C).

Stability: Shelf life surveillance studies of the intact bottle are on-going. Current data indicates lapatinib is stable for at least 2 years at controlled room temperature (15°C - 30°C).

RECOMMENDED ELEMENTS OF A SCIENTIFIC PROTOCOL
(Noted sections should only be included as applicable to your research)

Route of Administration: Oral on an empty stomach (either 1 hour before or 1 hour after meals).

Kool-Aid Flavored Suspension

Prepare Lemonade or Tropical Punch Kool-Aid as directed on the package. Place 2 or 4 oz of Kool-Aid (room temperature or refrigerated) in a glass container, then add six 250 mg lapatinib tablets to the container. Cover the container, let it stand for 5 minutes, and then stir the mixture intermittently for 10-20 minutes or until the tablets are completely broken up. Stir the container for 5 seconds then administer. Rinse the container with a 2 oz aliquot of water and administer (total of 4-6 oz of liquid is dispensed).

Suspension in Water

Place 4 oz of water in a glass container, then add six 250 mg lapatinib tablets to the container. Cover the container, let it stand for 5 minutes, and then stir the mixture intermittently for 10-20 minutes or until it is fully dispersed. Stir the container for 5 seconds then administer. Rinse the container with a 2 oz aliquot of water and administer (total of 6 oz of liquid is dispensed).

Prohibited Medications

Lapatinib is a substrate for CYP3A4. Inducers and inhibitors of CYP3A4 may alter the metabolism of lapatinib. The following list of CYP3A4 inducers and inhibitors are prohibited from screening through discontinuation from study.

Drug Class	Specific Agents	Wash-out ¹
CYP3A4 Inducers		
rifamycin antibiotics	rifampicin, rifabutin, rifapentine	2 weeks
anticonvulsants	phenytoin, carbamazepine, barbiturates (e.g., phenobarbital)	
antiretrovirals	efavirenz, nevirapine, tipranivir, etravirine	
glucocortical steroids (oral only)	cortisone (>50 mg), hydrocortisone (>40 mg), prednisone or prednisolone (>10 mg), methylprednisolone or triamcinolone (>8 mg), betamethasone or dexamethasone (>1.5 mg) ²	
other	St. John's Wort, modafinil	
CYP3A4 Inhibitors		
antibiotics	clarithromycin, erythromycin, troleandomycin, flucloxacillin	1 week
antifungals	itraconazole, ketoconazole, fluconazole (>150 mg daily), voriconazole	
antiretrovirals	delaviridine, nelfinavir, amprenavir, ritonavir, indinavir, saquinavir, lopinavir, atazanavir	
calcium channel blockers	verapamil, diltiazem	
antidepressants	nefazodone, fluvoxamine	

RECOMMENDED ELEMENTS OF A SCIENTIFIC PROTOCOL
(Noted sections should only be included as applicable to your research)

gastrointestinal agents ³	cimetidine	
fruit juices	grapefruit, star fruit, and papaw	
other	amiodarone	
Miscellaneous		
antacids	Mylanta, Maalox, Tums, Rennies	1 hour before and after dosing
herbal supplements ⁴	ginkgo biloba, kava, grape seed, valerian, ginseng, echinacea, evening primrose oil	2 weeks

1. Time period between last dose of listed drug and first dose of lapatinib, required to avoid drug-drug interaction potential for toxicity (inhibitors) or loss of efficacy (inducers) that could make the patient unevaluable. Clinically appropriate substitution of drugs not on the list is recommended.
2. A standard 3-5 day course of dexamethasone at a dose following the institutions standard of care for the prevention and/or treatment of platinum-induced nausea and vomiting is allowed. Glucocortical steroid oral dose equivalents (in parentheses) to dexamethasone 1.5 mg (or less) given daily are allowed. Intravenous dosing should be considered if clinically appropriate.
3. Emetogenic chemotherapy may require 3-4 daily doses of aprepitant. CYP3A4 inhibition by oral (not IV) aprepitant may require a concurrent dose reduction of 1-2 lapatinib tablets.
4. This list is not all-inclusive; therefore, for herbal supplements not listed, please contact a Novartis Medical Monitor or Clinical Scientist.

NOTE: If future changes are made to the list of prohibited medications, formal documentation will be created and stored with the study file. Any changes will be communicated to the investigative sites in the form of a letter.

Agent Accountability

